**Project Title: The Impact of Fruit and Vegetable Enzyme
Supplementation on Aerobic Capacity, and Blood
Biochemical Values Following Very Low Volume High-
Intensity Interval Exercise - Feasibility Study of Exercise
Design Using Motion-Sensing Video Games**

Study Protocol

File date : 15 / August / 2023

Introduction

Exercise represents a paradoxical element in health management, offering substantial benefits yet posing potential risks if not properly moderated [1, 2]. High-intensity exercise, while efficacious in improving various health parameters, can lead to oxidative stress, muscle damage, and inflammation [3, 4]. The oxidative stress primarily arises from increased reactive oxygen species production during intensive physical activities [5]. Moreover, exercise-induced fatigue serves as a protective mechanism against overexertion and consequent injuries [6, 7]. In contemporary fitness regimes, HIE, particularly the Tabata training method, has gained prominence for its effectiveness in enhancing aerobic power, fat oxidation, and muscular endurance [8-10]. These attributes are especially crucial for the elderly population, a demographic that significantly benefits from regular physical activity [11-13].

Exergaming, an innovative blend of physical exercise and interactive gaming, has emerged as a transformative approach to fitness, especially in engaging diverse age groups in regular physical activity. Its efficacy in enhancing key fitness parameters like aerobic capacity, agility, and coordination, coupled with its ability to make exercise more enjoyable, has been well documented [14-16]. This fusion of technology and exercise not only caters to the digital age but also opens avenues for personalized fitness experiences, adaptable to various demographic needs [17, 18]. While exergaming has been effective across a range of ages, its application in elderly populations presents unique opportunities and challenges. As the elderly population seeks safe, engaging, and effective exercise methods, exergaming could offer a solution that aligns with these requirements. However, integrating HIE concepts into exergaming for the elderly remains a relatively uncharted territory. HIE, known for its efficiency in improving cardiovascular health and metabolic function, could significantly benefit older adults, particularly in terms of enhancing functional capacity and overall quality of life [12, 19].

The potential of HIE within exergaming for the elderly hinges on the balance between intensity and safety. While HIE is beneficial, it is crucial to adapt its intensity to suit the physiological capabilities and limitations of older individuals. Research indicates that tailored HIE programs can be both feasible and beneficial for older adults, leading to improvements in cardiovascular health, muscle strength, and metabolic function [20, 21]. Integrating these concepts into exergaming could further enhance adherence and enjoyment, crucial factors in maintaining regular exercise habits in this demographic. Furthermore, the interactive and immersive nature of exergaming can address common barriers to exercise among the elderly, such as lack of motivation or fear of injury. By providing a safe, controlled environment for engaging in HIE, exergaming can potentially transform the perception and experience of high-intensity workouts for older adults. This is particularly pertinent given the increasing need for innovative exercise interventions that cater to the aging global population [11].

Nutritional supplementation, especially with natural fruit and vegetable enzymes, presents a promising avenue in augmenting exercise performance through their antioxidant, anti-inflammatory, and metabolic benefits [21-28]. Such supplementation could potentially optimize lactate metabolism and enhance muscle function during exercise. Recent advancements in nutritional science have highlighted the significant role of natural fruit and vegetable enzymes in enhancing exercise performance. These

enzymes are increasingly recognized for their multifaceted health benefits, including their antioxidant, anti-inflammatory, and metabolic-enhancing properties [21, 22]. Notably, their potential impact on exercise physiology, particularly in the context of high-intensity workouts, offers a new perspective on improving athletic performance and recovery.

One of the critical areas where these enzymes show promise is in the modulation of lactate metabolism. Lactate, often produced in higher quantities during intense physical activity, can lead to fatigue and decreased muscle efficiency. The traditional view of lactate as merely a byproduct of anaerobic metabolism has evolved, with current research acknowledging its role as a valuable energy source during prolonged exercise [23]. This shift in understanding opens up new avenues for utilizing enzyme supplementation to optimize lactate utilization. Enzymes such as bromelain and papain, found in pineapples and papayas respectively, have been studied for their potential in improving lactate metabolism. These enzymes are known to facilitate faster clearance of lactate from the bloodstream, thereby enhancing recovery and reducing fatigue [26, 28]. Furthermore, the antioxidant properties of these enzymes play a crucial role in combating oxidative stress, which is often elevated during intense exercise regimes [24, 25]. This reduction in oxidative stress is not only beneficial for immediate recovery but also contributes to long-term muscle health and function. Moreover, the anti-inflammatory actions of these natural enzymes can mitigate the inflammatory response often triggered by high-intensity exercise [27]. By reducing inflammation, these enzymes may enhance muscle recovery and function, thus allowing for more efficient and prolonged exercise performance. This aspect is particularly relevant in training regimens where recovery is as crucial as the exercise itself.

The primary aim of this feasibility study is to examine the effects of fruit and vegetable enzyme supplementation on aerobic capacity and blood lactate response in elderly individuals engaged in HIIE through an exergaming framework. This study is dual-faceted, focusing firstly on the physiological responses and feasibility of an exergaming-HIIE regimen tailored for the elderly, and secondly, on the impact of enzyme supplementation on enhancing these exercise outcomes.

Methods

Participants And Experimental Design

All participants reported a regular exercise habit (3 times per week within the past year). They also completed the Physical Activity Readiness Questionnaire and confirmed no history of upper limb skeletal muscle injury or major injury. Participants were instructed to avoid strenuous activities and the intake of caffeine or muscle-enhancing supplements for 24 hours prior to the experiment. Before the study commenced, all participants provided personal information, completed health questionnaires, disclosed personal medical history, and signed informed consent forms.

The 16 participants underwent the Exergaming HIIE test as an initial assessment (pre-test). Participants engaged in a 5-minute warm-up on a stationary bike, followed by HIIE using the Nintendo Switch Ring Fit Adventure design. The training method was adapted from the research of [8, 9] and consisted of 8 sets of 20 seconds of

maximum effort exercise with 30 seconds of complete rest between each set, resulting in a total exercise time of 370 seconds. The HIEE design incorporated training modes targeting the deltoid, pectoralis major, latissimus dorsi, and quadriceps muscles in the Nintendo Switch Ring Fit Adventure. Blood lactate levels, heart rate, and ratings of perceived exertion were recorded before, during, and after exercise, and training load was quantified using TRIMP. Participants were matched and divided into two groups, the enzyme group, and the placebo group, based on their blood lactate levels during HIEE. Each group comprised 8 individuals. Supplementation with vegetable and fruit enzymes or maltodextrin commenced three days after the pre-test and lasted for a total of 14 days. On the 14th day, following the completion of supplementation, the participants underwent the Exergaming HIEE test as a post-test.

Ethical Considerations

The human research ethics committee of the local university approved this study, which was also approved by the human research ethics committee of the National Cheng Kung University, Taiwan. (Approval No. NCKU HREC-E-112-419-2). Users volunteered for this study and agreed to participate by signing an informed consent form.

Supplementation Protocol

After the pre-test, the enzyme group consumed 30 mL of vegetable and fruit enzymes (The contents include needle-leaf cherries, cherries, apples, cranberries, blackberries, black currants, blueberries, beets, broccoli, cabbage, carrots, Concord grapes, cranberries, elderberries, kale, oranges, peaches, papayas, parsley, pineapples, raspberries, red currants, spinach, and tomatoes, etc.) (Enzyme Village, Chiayi, Taiwan) mixed with 150 mL of water twice a day (at breakfast and dinner) for 14 consecutive days. The placebo group followed the same protocol but consumed malt syrup (Amazon, USA) instead until the end of the study. Participants returned to the laboratory each morning to receive the daily supplement, which was administered on-site. Following supplementation, participants reported their dinner intake to the researchers, ensuring compliance with the prescribed supplementation regimen.

Exergaming HIEE Test-Combination Of Exergaming And HIEE

Participants in this experiment engaged in HIEE using the Nintendo Switch Ring-Con within a laboratory environment. All participants completed pre-test and post-test assessments on the same day. The exergame employed in this study was 'Nintendo Switch Fitness Adventure,' which ingeniously blends exercise with an adventure narrative to deliver both physical workouts and gaming enjoyment concurrently. This game is noted for its intuitive, user-friendly interface that accommodates players of all ages. It incorporates a specialized fitness ring -a smart accessory that connects to the Nintendo Switch console. The sensor system utilized two Nintendo controllers: one mounted on the exercise ring and the other secured to the participant's thigh to enhance gameplay interaction. Through the Ring-Con, participants engaged in diverse physical activities such as weightlifting, yoga, and aerobic exercises. The fitness ring sensor accurately captures and integrates players' movements into the game. The gameplay involves unlocking levels and engaging in fitness challenges that are achieved through actual physical activities. It offers a wide range of exercise routines targeting various

muscle groups and provides engaging gaming challenges. The exercise protocol included eight sets of 20-second high-effort exercises, interspersed with 30-second rest intervals, totaling 370 seconds of active exercise time. Specifically, the fitness game mode used was the Adventure Mode in 'Ring Fit Adventure,' comprising exercises targeting the pectoralis major, latissimus dorsi, deltoids, and quadriceps muscles (Figures 2).

[figure not shown]

Figure 2. Experimental flowchart. Ex-: bout of HIIE test; Post-5 min: after 5 minutes of HIIE test; Post-10 min: after 10 minutes of HIIE test. Asterisk (*) indicates lactate test. Asterisk (#) indicates test heart rate and RPE.

Blood Lactate Test

The blood lactate was measured at five time points: before exercise, after the fourth and eighth bouts of exercise, and at 5 and 10 minutes after exercise. The blood lactate were analyzed using a Biosen Cline blood analysis system (EKF-diagnostic, Germany). Capillary blood samples of 10 μ L were collected and added to red blood cell lysis reagent and stored at low temperature until analyzed. Prior to analysis, instrument standardization and test calibration were performed, and the coefficient of variation was determined to be $\leq 1.5\%$. The detection range for blood lactate was 0.5-40 mM [31].

Training Impulse

In this study, the exercise load was represented by the TRIMP [32], which is calculated as the product of exercise intensity and duration. To accommodate the convenience of the experiment, two different TRIMP calculation methods were used, including % HRmax (objective) and RPE (subjective). At the end of each exercise bout (8 bouts in total) and during the recovery period before the next bout (7 bouts in total), participants were asked to report their RPE, and their heart rate was recorded. This process was repeated 8 times.

% HRmax Calculation Method

During the entire HIIE, the participant's HR was recorded every 5 seconds using a heart rate monitor (iHeart Polar, Taiwan) to calculate % HRmax. The block TRIMP

method developed by S. Edwards [33] was used, which divides the exercise intensity into 5 blocks with corresponding weighting factors (Table 1). The weighted score of each block was multiplied by the exercise time (min) and then summed to obtain the exercise load (arbitrary unit [AU]). The calculation formula is as follows: Exercise load = (Z1 exercise time × 1) + (Z2 exercise time × 2) + (Z3 exercise time × 3) + (Z4 exercise time × 4) + (Z5 exercise time × 5)

Table 1 The Edwards' block TRIMP calculation method

Zone	Intensity	Weighted score
Z1	50%-60% HRmax	1
Z2	60%-70% HRmax	2
Z3	70%-80% HRmax	3
Z4	80%-90% HRmax	4
Z5	90%-100% HRmax	5

RPE Calculation Method

The TRIMP calculation method of Foster, Hector [34] and Foster, Florhaug [35] was used to calculate the exercise load by multiplying the RPE value of each exercise segment by the exercise time and summing them up. The RPE scale used in this method was the CR-10 version modified by Foster, Florhaug [35] based on Borg, Ljunggren and Ceci [36] (Table 2). The calculation formula is as follows: Exercise load (AU) = Borg's CR-10 RPE score × exercise time (min)

Table 2. Borg's CR-10 RPE

0	Rest
1	Very, very easy
2	Easy
3	Moderate
4	Somewhat Hard
5	Hard
6	
7	Very Hard
8	
9	
10	Maximal

Statistical Analysis

All the data were analyzed by SPSS for Windows 20.0. Data are expressed as the mean \pm standard deviation (SD) and 95% confidence interval (95% CI). A mixed design two-way analysis of variance (ANOVA) (group \times time) was used to compare the variables of lactate, heart rate and training impulse between two groups before and after the 14-days of supplementation. Graphs were generated using GraphPad Prism 8.0 (GraphPad Software, San Diego, California, USA). Cohen's conventions for ES (Cohen d) were calculated by the G*Power 3.1 software program (Heinrich-Heine-Universität, Düsseldorf, Germany), where the ESs of 0.2, 0.5, and 0.8 are considered small, medium, and large, respectively. Statistical significance was set as $p < 0.05$.

References

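### Aerobic capacity is in the title and the primary aim, but the plan describes no measure of it and declares no surrogate, so that part of the aim cannot be answered

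*Combined protocol and SAP*

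**What the plan says.** The title announces an effect of "Supplementation on Aerobic Capacity, and Blood" biochemical values. The last paragraph of the Introduction gives the primary aim: to "examine the effects of fruit and vegetable enzyme supplementation on aerobic capacity and blood lactate response in elderly individuals" who exercise through an exergame. Aerobic capacity and lactate response appear there as two separate items. The next sentence describes the study as "focusing firstly on the physiological responses and feasibility of an exergaming-HIIE regimen tailored for the elderly", and secondly on whether supplementation enhances those outcomes.

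Under Participants And Experimental Design, the measurements are: "Blood lactate levels, heart rate, and ratings of perceived exertion were recorded before, during, and after exercise, and training load was quantified using TRIMP". The test is eight 20-second sets of "maximum effort exercise with 30 seconds of complete rest between each set".

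The Blood Lactate Test section lists five samples per test: before exercise, after bouts four and eight, and 5 and 10 minutes after exercise. Under Training Impulse, "the exercise load was represented by the TRIMP", calculated once from heart rate and once from RPE. The Statistical Analysis section applies a two-way mixed ANOVA (group × time) to lactate, heart rate and training impulse.

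**The concern.** A stated primary effect needs an outcome that measures it. Aerobic capacity, the first construct in both the title and the aim, appears to have none. If so, any sentence about it in the report would have to be inferred from lactate, heart rate, RPE or TRIMP. All four also move with how hard a participant tries, so a lower value at the post-test could mean better capacity or simply less effort. No analysis of the planned data can supply the missing measurement.

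A lesser matter concerns the lactate part of the aim. Five samples are taken per test and none is named as the one that answers the aim, so the choice could be made after the results are known.

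**Working it through.** The plan gives no figure to reproduce on this point, and the main claim needs no calculation beyond a count. The check is a comparison of the aim with every measurement section.

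**1. Where the term occurs.** In the body text, aerobic capacity appears in the title, in one Introduction sentence about exergaming ("Its efficacy in enhancing key fitness parameters like aerobic capacity, agility, and coordination") and in the primary aim. It does not appear in the Methods or Statistical Analysis text. The only related word there is the adjective aerobic, used of a type of game activity in the Exergaming HIEE Test section. Maximal oxygen uptake appears only in the title of a cited reference.

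**2. What is measured and analysed.**

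| Variable | Where described | How the plan presents it | In the ANOVA list |
|---|---|---|---|
| Blood lactate | Blood Lactate Test | a separate item beside aerobic capacity in the aim | yes |
| Heart rate | Training Impulse; % HRmax Calculation Method | basis of one TRIMP version | yes |
| RPE | RPE Calculation Method | basis of the other TRIMP version | only through TRIMP |
| TRIMP | Training Impulse | exercise load | yes |

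Of the three recorded variables (lactate, heart rate, RPE), 0 are defined as aerobic capacity. Of the three analysed variables (lactate, heart rate, training impulse), 0 are. Declared surrogates: 0. The image of Figure 2 is not available in the text reviewed, but its legend marks only lactate, heart rate and RPE, so the missing image is unlikely to explain the gap.

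**3. Whether TRIMP could fill the gap.** One version is RPE × exercise time. The other is the sum over heart-rate zones of zone weight × time in zone. The schedule is the same for everyone at both tests: 8 × 20 s + 7 × 30 s = 160 s + 210 s = 370 s. With total time fixed, the RPE version can change only if RPE changes, and the heart-rate version only if heart rate changes. TRIMP therefore carries nothing beyond those two variables.

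**4. Whether the test itself could serve as a capacity test.** Its duration is fixed and its intensity is whatever the participant gives as maximum effort. It is not run to exhaustion, and no work output is described as an outcome. Without work output, a change in heart rate, RPE or lactate cannot be set against the amount of work done.

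**5. The lactate part.** Lactate is measured at both tests and included in the ANOVA, so this part of the aim has data and an analysis. What is left open is which of the five values, or which summary of them, is used. The wording compares the groups before and after supplementation but does not define the levels of time. They could be pre-test and post-test, or the sampling points within a test.

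**The case against.** Three arguments deserve an answer.

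**Loose wording in a feasibility study.** The sentence after the aim speaks of physiological responses and feasibility, and the recorded variables fit that. On this reading, aerobic capacity is shorthand for exercise response. What stands is that the defect lies in the match between aim and outcomes, can be cured in the text, and invalidates no planned analysis of lactate, heart rate or TRIMP. But the sentence neither supplies a measure nor withdraws the aim, and the title repeats the term.

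**Indirect indices.** Heart rate or lactate at a standard exercise dose might be argued to reflect fitness. The plan does not make that argument: it lists lactate beside aerobic capacity and labels TRIMP as load. Nor does it show the dose to be standard, since effort is maximal and no work output is described. Justifying and pre-specifying a surrogate would be a legitimate route in principle, but the documents contain nothing on which to base one.

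**Stronger readings that go too far.** A reader might infer that external work went unrecorded. The Exergaming HIEE Test section says the ring sensor captures movement for the game, so the documents support only that no work output is described as recorded for the study or analysed. A reader might also infer that five lactate samples mean five separate tests, and attach an inflated false-positive rate. The plan never says each sample is tested separately, one of the five precedes exercise and so is not a response to it, and the meaning of time is open. The documents support under-specification, not a particular error rate.

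**Conclusion.** The concern holds for the aerobic capacity part of the primary aim. One of its two constructs has no measure, no declared surrogate and no place in the analysis. This should be corrected, because an aerobic capacity statement in the report would have no support in the plan. The conclusion rests on reading the Methods and Statistical Analysis sections as complete; they show no sign of removed text, and it depends on no statistical assumption.

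A reader might infer that the whole primary aim fails. It does not: blood lactate is measured and analysed, and that part remains answerable.

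The lactate specification is a separate and minor point. The plan does not make clear which lactate quantity enters the ANOVA or what time means. The main conclusion does not depend on it.

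**What to change.** **Main change, dated and disclosed:**

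- State that aerobic capacity was not measured, and remove it from the title and primary aim.
- Restate the aim as the effect of supplementation on blood lactate response to the exergaming test, with heart rate, RPE and TRIMP as secondary measures of internal load.
- State that no aerobic capacity conclusion will be drawn from lactate, heart rate, RPE or TRIMP.
- Note as a limitation that no work output is described, so differences in lactate cannot be separated from differences in work done.

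**Minor change:** before post-test results are examined, name one lactate quantity and define time as pre-test versus post-test, so that the group × time interaction tests that quantity. The rationale in the Introduction is clearance ("These enzymes are known to facilitate faster clearance of lactate from the bloodstream"), so the 10-minute sample, or the fall from the end of bout eight to 10 minutes, would be consistent with it. Report the other samples descriptively. If post-test results have already been examined, say so and label the lactate comparisons exploratory. The Methods describe both tests in the past tense, so this may be the case that applies.

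**Cost:** no new measurement is needed. The claim becomes narrower, a single lactate quantity may miss an effect at another sampling point, and the ethics committee may need to be notified. Keeping the present aim by adding an aerobic capacity test at both visits is possible only if the pre-test has not yet been done, and would need ethics review.

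### The injury criterion names only the upper limb, although the test also works the quadriceps at maximum effort, so a non-major leg injury passes the stated rule

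*Combined protocol and SAP*

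**What the plan says.** The only injury rule is in Methods, Participants And Experimental Design, where participants "confirmed no history of upper limb skeletal muscle injury or major injury". It has two parts: muscle injury of the upper limb, and a second category of major injury that is neither defined nor tied to a body region.

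The same section says the exercise used "training modes targeting the deltoid, pectoralis major, latissimus dorsi, and quadriceps muscles". The section on the Exergaming HIEE Test repeats the list: "comprising exercises targeting the pectoralis major, latissimus dorsi, deltoids, and quadriceps muscles". The design section also describes a 5-minute warm-up on a stationary bike, then 8 sets of 20 seconds at maximum effort.

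Other screening is mentioned. "They also completed the Physical Activity Readiness Questionnaire", and participants also "completed health questionnaires, disclosed personal medical history, and signed informed consent forms". They reported exercising 3 times per week over the past year. The Introduction gives the population; the aim concerns "blood lactate response in elderly individuals engaged in HIIE through an exergaming framework".

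On timing, supplementation "commenced three days after the pre-test and lasted for a total of 14 days". The second test is placed as follows: "On the 14th day, following the completion of supplementation, the participants underwent the Exergaming HIEE test as a post-test".

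**The concern.** An injury criterion normally covers the body parts that the test will load. Here it names the arms, but the test loads arms, trunk and thighs. The protocol gives no reason for naming one region and leaving out another that is worked in the same session.

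Participant safety is at stake. An older person with, say, a recent thigh strain or a painful knee that nobody would call major can truthfully confirm the criterion and then be asked for maximum-effort work that includes the quadriceps, once before and once after supplementation. A leg injury that arises between the two tests is a second route to the same situation, because the text describes no repeat of the injury question before the post-test.

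**Working it through.** The main check is a comparison of statements. The arithmetic only describes exposure and timing.

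**1. Region screened against region worked.**

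| Target muscle group | Region | Covered by the stated injury rule? |
|---|---|---|
| Deltoid | Shoulder | Yes, upper limb |
| Pectoralis major, latissimus dorsi | Chest and back, acting on the arm | Broadly, upper limb |
| Quadriceps | Thigh | Only if the injury is major |

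The quadriceps is 1 of 4 named groups and the only one in the leg. The cycling warm-up also uses the legs.

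**2. Two readings of the rule.** The phrase on major injury can be read as (a) major injury at any site, or (b) major injury of the upper limb. Under (a), a major leg injury is excluded and a lesser one is not. Under (b), no leg injury is excluded. A non-major leg injury passes under both. Reading (a) is the more natural one and is used here.

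**3. Whether another statement closes the gap.** The readiness questionnaire, the health questionnaires and the medical history could each reveal a leg problem. Their content is not given, and no answer is linked to exclusion or to review by the investigator. Exercising 3 times per week does not rule out a minor or moderate leg injury. No lower-limb criterion appears elsewhere in the documents.

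**4. Exposure.** Work per test: 8 × 20 s = 160 s. Rest between sets: 7 × 30 s = 210 s. Total: 160 + 210 = 370 s, which reproduces the protocol's figure and shows that it includes the rests. Over two tests the work is 2 × 160 = 320 s. The documents do not say how many of the 8 sets load the legs.

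**5. Gap between the tests.** Supplementation starts 3 days after the pre-test and the post-test is on its 14th day. Counting the first supplement day as day 1, the gap is 3 + 13 = 16 days. The Exergaming HIEE Test section says both assessments were completed on the same day, but this cannot mean one calendar day when 14 days of supplementation lie between them.

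**6. Existing contact.** Under Supplementation Protocol, participants attend the laboratory every morning for the supplement, so a question on the post-test day needs no new visit.

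**The case against.** The strongest reply is that much of this is inferred from silence. The readiness questionnaire is by its name a screen for fitness to exercise, and it is mentioned in the same sentence as the injury rule. Staff see participants daily, the work is brief and done in a laboratory, and heart rate and perceived exertion are recorded around every bout. The section is also a past-tense description of participants, not a formal exclusion list. All of this is fair. It lowers the severity, and it means the documents cannot show that an injured person would in fact be tested. It does not alter the wording: the one explicit injury rule names the arms and omits the legs.

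Three stronger readings are tempting, and the documents do not support them.

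- *The legs are not screened at all.* A reader might infer this, but major injury plausibly covers any site, so only lesser leg injuries are left out.
- *Injured people are likely to be enrolled.* One could assume that 2% to 20% of volunteers have such an injury and compute, for 16 people, 1 − (1 − p)^16 = 28% to 97% for at least one enrolled. That range has no source in the documents, and the formula assumes that the questionnaires exclude nobody. Even then it gives a chance of enrolment, not of harm.
- *A new injury before the post-test would go unnoticed.* The text describes no repeat question, but with daily attendance that does not establish that nobody would ask.

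**Conclusion.** The point holds in a limited form. As written, the criterion does not exclude a non-major lower-limb injury, although the test works the quadriceps at an intensity the design section calls maximum effort. The conclusion rests on the wording alone and survives either reading of major injury. It assumes only that the other screening carries no unstated rule about the legs; if it does, the remedy is to write that rule down.

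Severity is low. The exposure is 160 s of work per test, with an unstated share for the legs, done twice by each of 16 people about 16 days apart. No harm rate is claimed, because the documents give no injury frequency. The sample size, the group × time analysis of variance and the significance level are unaffected.

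**What to change.** Keep the upper-limb clause. Add after it: *no current or recent lower-limb muscle or joint injury that limits exercise*. End with: *no major injury at any site*. The investigators should state what time window recent means and what counts as major. The limit to current or recent injury that restricts exercise is deliberate: a lifetime ban on any limb muscle or joint injury would be too broad for an elderly sample.

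Ask the same question again at the morning visit on the post-test day, and let the investigator decide whether a person who reports a new injury is tested.

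Two small documentation edits fit alongside: say who reviews a positive readiness answer before the pre-test, and use one effort term, since the Exergaming HIEE Test section calls the same sets high-effort.

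The cost is a reworded eligibility line, one repeated question at a visit that already takes place, and an ethics notification. A few volunteers may be turned away; the documents do not allow that number to be estimated. A person held back from the post-test costs 1 of 8, or 12.5%, of that group. If testing is already complete, the wording serves any repeat or larger study of the same exercise design.
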